7 CONCURRENT MEDICATIONS

All subjects should be maintained on the same medications from screening through Visit 5 (Day 28), as medically feasible, with no introduction of new chronic therapies. Medication history will be collected for all drugs for the 30 days prior to screening. If any changes in concomitant medications are required due to AEs (i.e. illness, laboratory abnormalities, surgical procedures, etc.), the reason(s) for the change(s) must be documented. Subjects who require treatment for a pulmonary exacerbation during the course of the trial will remain in the study.

Subjects who have routinely taken more than 10 mg/day (or >20 mg on alternate days) of prednisone or other systemic corticosteroids 4 weeks prior to Visit 1 (Day -42 to -10) or who have taken these medications as needed within 72 hours prior to Visit 1 or 2 will be excluded from participation. Subjects may be re-screened once. For those subjects taking alternate month TOBI® or Cayston® therapy, on/off cycles must be timed such that a subject is at the same phase of a cycle at Visits 2, 3, 4, and 5.

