7.2 Prohibited

- Intravenous antibiotics from 14 days prior to the screening visit through Visit 2 (Day 1)
- Newly prescribed oral or inhaled antibiotics prescribed for acute symptoms from 14 days prior to the screening visit through Visit 2 (Day 1)
- Systemic corticosteroids prescribed for an acute issue or for chronic therapy if the dose exceeds a prednisone equivalent of 10 mg every day or 20 mg on alternate days (maximum allowable dose for chronic systemic corticosteroids is 20 mg of prednisone or its equivalent over a two day period) from screening through Visit 5 (Day 28)
- Hydroxychloroquine from screening through Visit 5 (Day 28)
- Other immunosuppressants from screening through Visit 5 (Day 28)
- The use of an investigational agent within 4 weeks prior to Visit 1 (Day -42 to -10)

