9.1 Clinical Assessments

9.1.1 Concomitant Medications

All concomitant medications and concurrent therapies will be documented at all study visits including an Acute Illness/Early Termination Visit when applicable. Dose, route, unit frequency of administration, and indication for administration and dates of medication will be captured for the 30 days prior to screening.

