10.15 Acute Illness/Early Termination Visit

1. Review and record RSSQ prior to any other study procedures
2. If Acute Illness or Early Termination Visit occurs before Visit 5, administer and review CFRSD prior to any other study procedures and record any AEs that occurred since last Visit or Telephone call
3. Review and record interval history
4. Review and record any changes to concomitant medications
5. Measure and record weight without shoes
6. Perform and record vital signs, including a blood pressure after the subject has been seated for 5 minutes
7. Perform and record oximetry
8. Perform a complete physical examination
9. Collect blood for clinical laboratory tests (comprehensive chemistry panel, ESR, hs-CRP, complete blood count with differential, direct bilirubin and LDH)
10. Collect urine for clinical laboratory test (urinalysis)
11. Collect urine for pregnancy test
12. Administer 3 puffs of albuterol 15 minutes prior to spirometry if subject performed a sputum induction during the study
13. Perform and record spirometry
14. Record any AEs that may have occurred during the study visit

For Healthy Volunteer Subjects:**10.16 Visit 1 (Screening Visit: Day -30 to -7)**

1. Review the study with the subject and obtain written informed consent and HIPAA authorization
2. Assign the subject a unique screening number
3. Record demographics and other baseline data
4. Record medical and surgical history
5. Record concomitant medications
6. Review inclusion/exclusion criteria
7. Perform and record vital signs, including a blood pressure after the subject has been seated for 5 minutes
8. Complete Donor History Questionnaire (DHQ)

9. Collect 32 ml blood for laboratory tests (infectious disease markers, CMV, CF mutations). Collect 2 ml blood for serum pregnancy test if applicable.
10. Record any AEs that may have occurred during the study visit from the time of consent

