15.1 Data Sets Analyzed

All eligible subjects who are enrolled into the study and receive at least one dose of the investigational product (the Safety Population) will be included in the safety analysis. The analyses will be conducted on all data available. Subjects with missing data for a particular analysis will not be included as applicable.

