15.3 Analysis of Primary Endpoint

The primary endpoint of this study is to determine the maximum tolerate dose among 1×10^6 hMSCs/kg, 3×10^6 hMSCs/kg, and 5×10^6 hMSCs/kg. Safety data will be analyzed at both the individual level and the dose cohort level. Safety will be evaluated using reports of adverse events (AE) and measurements of vital signs, oxygen saturation, pulmonary function, laboratory parameters and adverse events associated with procedures (sputum induction for those subjects unable to spontaneously expectorate sputum and optional bone marrow aspiration). All measurements will be reported at each time point, changes from Baseline and from the previous time point will be summarized at each time point. Premature withdrawals and reasons of withdrawals will be listed.

Clinically significant AEs and alterations in vital signs, oxygen saturation, and pulmonary function at baseline, 30 minutes, 4 hours and 24 hours after the infusion will be summarized by patient and by dose cohort using frequency/percentage and mean or median/range.

Overall AEs and SAEs in each dose cohort will be coded by body system and MedDRA classification term using frequency and percentage. Frequency and percentage of all grades and grades ≥ 3 will be reported.

AEs among dose cohorts will be compared using Fisher's exact test. All clinically significant vital sign and physical examination changes as well as laboratory test abnormalities will be presented in AE listings.

Mean or percentage of clinically significant AEs, alterations in vital signs (including decreases in systolic blood pressure ≥ 20 mmHg or diastolic blood pressure ≥ 10 mmHg), spirometry measurements (FEV₁ %, FEV₁ (Liters), FEF₂₅₋₇₅), sputum quantitative microbiology (bacterial colony forming units) and hematology, comprehensive chemistry, ESR, hs-CRP and urinalysis results measured at Baseline and at the follow-up visits will be graphically presented.

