18 APPENDIX I: DEFINITION OF A PULMONARY EXACERBATION (MODIFIED FUCHS CRITERIA)⁹⁵

An exacerbation of respiratory symptoms is defined as a subject undergoing a change in antibiotic therapy for any 4 of the following 12 signs or symptoms:

1. Change in sputum
2. New or increased hemoptysis
3. Increased cough
4. Increased dyspnea
5. Malaise, fatigue, or lethargy
6. Temperature above 38 °C
7. Anorexia or weight loss
8. Sinus pain or tenderness
9. Change in sinus discharge
10. Change in physical examination of the chest
11. Decrease in pulmonary function by 10 percent or more from a previously recorded value
12. Radiographic changes indicative of pulmonary infection

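### The Day 7 and Day 28 CFU summaries do not separate cultures taken after a new antibiotic, so a treated exacerbation can appear as a CFU fall in a small cohort mean

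*Combined protocol and SAP*

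**What the plan says.** Section 5.1 lists change in sputum CFU from Day 1 to Day 7 and to Day 28 as one component of the primary safety endpoint. Section 9.3.4 schedules quantitative culture at those three visits only. Section 15.3 states that safety data are analysed by individual and by dose cohort, and it names "sputum quantitative microbiology (bacterial colony forming units" among the measures whose mean or percentage is graphed at Baseline and follow-up. Section 15.1 sets the data rule: "The analyses will be conducted on all data available".

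For antibiotics, Section 7.2 prohibits "Newly prescribed oral or inhaled antibiotics prescribed for acute symptoms from 14 days prior to the screening visit through Visit 2 (Day 1"; the ban on intravenous antibiotics ends at the same visit. Section 7 asks for stable medication through Day 28 where medically possible. When an AE forces a change, "the reason(s) for the change(s) must be documented". It also says: "Subjects who require treatment for a pulmonary exacerbation during the course of the trial will remain in the study".

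Appendix I defines an exacerbation as "a subject undergoing a change in antibiotic therapy for any 4 of the following 12 signs or symptoms". The Acute Illness Visit (Section 10.15) has no sputum step. It mentions sputum only to decide on bronchodilator use: "Administer 3 puffs of albuterol 15 minutes prior to spirometry if subject performed a sputum induction during the study". The sputum rows of Appendix II are also empty for that visit.

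**The concern.** The protocol gives special attention to exacerbations because a cell product that damps inflammation might let infection worsen. If that happens and is treated, the treatment can lower the CFU count. By the Appendix I definition, every counted exacerbation involves an antibiotic change. When treatment starts between two culture visits, the next scheduled culture falls during or after the course, and no earlier culture is scheduled to record a rise.

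The possible distortion therefore has a direction: the event under watch can move the CFU mean the favourable way. There is no control group, and each of the first three cohorts has 3 subjects, so a cohort mean cannot separate the antibiotic's effect from that of the cells. A reader could take a fall as reassurance about infection, or as support for the antimicrobial action proposed in the background sections.

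**Working it through.** **Does any rule separate these cultures?**

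- Section 7.2 stops applying to acute antibiotics after Day 1.
- The same-cycle-phase rule in Section 7 covers alternate-month inhaled therapy, not a new acute course.
- The Synopsis restriction on treatment changes between Visits 1 and 5 concerns chronic therapy.
- The stability request in Section 7 is a goal for conduct, not an analysis rule.
- Sections 15.1 to 15.4 contain no flag, stratum or sensitivity display for antibiotic use.

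Pooling is an inference from the all-available-data rule combined with the absence of any antibiotic rule; no sentence states it outright. It does not affect every illness. One first recognised at Visit 3 or Visit 5 can be cultured that day.

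**Plan figures.** The plan gives no exacerbation rate, CFU standard deviation, expected CFU change or scale for averaging CFU, so there is no figure to reproduce. Table 1 adds up: 3 + 3 + 3 + 6 = 15. Cohort 3 plus Cohort 4 gives n = 9 at the top dose if 5 x 10^6/kg is the MTD.

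**Chance of at least one treated subject (rates assumed).** With r treated exacerbations per subject-year, P = 1 - exp(-n x r x d/365).

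| n, window | r = 0.5 | r = 1 | r = 2 |
|---|---|---|---|
| 3, 28 days | 0.109 | 0.206 | 0.369 |
| 9, 28 days | 0.292 | 0.499 | 0.749 |
| 15, 28 days | 0.437 | 0.684 | 0.900 |
| 15, 7 days | 0.134 | 0.250 | 0.437 |

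Example: n = 3, r = 1, d = 28 gives 1 - exp(-84/365) = 0.206. Assuming instead a 5% to 30% risk per subject by Day 28, 1 - (1 - p)^n gives 14% to 66% for n = 3 and 54% to 99.5% for n = 15. The answer depends on the assumption.

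**Shift in the mean (also assumed).** Suppose CFU is averaged on the log10 scale, one subject falls by D and the others change by u. The mean change is (-D + (n - 1)u)/n.

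- u = 0, D = 0 to 2: the mean moves by 0 to -2/3 = -0.67 for n = 3, and by 0 to -2/9 = -0.22 for n = 9.
- u = +0.3, D = 2: (-2 + 0.6)/3 = -0.47 for n = 3, although the other two subjects rose. For n = 9 it is (-2 + 2.4)/9 = +0.04.
- With u = +0.3 the mean turns negative once D exceeds 0.3(n - 1): 0.6 for n = 3, 1.5 for n = 6 and 2.4 for n = 9.

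**How full a flagged cell would be.** With p = 1 - exp(-r x 28/365), the binomial probability of 0 or 1 treated subject is 0.996 / 0.984 / 0.945 for n = 3 and 0.957 / 0.861 / 0.627 for n = 9, at r = 0.5 / 1 / 2.

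**The case against.** The strongest reply is that a descriptive safety summary of all observed data is legitimate, and that a count taken after treatment is a true value for that day. Infectious harm has its own measures: exacerbation counts, AEs, the RSSQ, the CFRSD and the Acute Illness Visit. The DMC reviews each cohort before the next opens (Section 14). CFU is not a secondary endpoint (Section 5.2), and the models in Section 15.4 cover inflammatory biomarkers only. Section 15.3 already promises individual-level reporting, and Section 15 defers detail to a later SAP. All of this stands, and it keeps the point small. It does not tie an antibiotic course to a particular culture, which is what a reader of the cohort mean needs.

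The probabilities above also lean high. They treat every subject as a sputum producer, although a subject with no sputum at Baseline gives none later (Section 9.1.7). They count illness first seen at Visit 5. They also apply a constant rate to subjects selected as clinically stable.

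A reader might infer from Section 9.1.1, where "dates of medication will be captured for the 30 days prior to screening", that antibiotic use during the study is not captured well enough to apply a flag. The documents do not support that. Read with Section 7, the sentence sets the look-back before the study. Section 10 has medication changes recorded on Day 2, at Visits 3, 4 and 5 and at the Acute Illness Visit; at Visits 3 and 5 that step is listed before sputum collection. Section 9.1.11 adds AE start and stop dates and treatment.

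**Conclusion.** The point holds as a cheap improvement to a descriptive display. Under Sections 15.1 and 15.3 as written, an exacerbation treated between culture visits can appear as a CFU fall in a small, uncontrolled cohort mean. That fall is neither evidence that infection did not worsen nor evidence of an antimicrobial effect.

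Its size cannot be derived from the documents. The 11% to 37% chance for a cohort of 3, and the shift of 0 to -0.67 log10, rest on assumed rates and an assumed treatment effect whose range includes zero. With no standard deviation given, it is unknown whether such a shift would exceed ordinary sputum variation.

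Two stronger conclusions might be drawn, and neither is supported. One is that the trial would miss infectious harm or that its safety conclusion is compromised. Exacerbations and AEs are counted regardless of CFU, CFU has no planned test, and DLT/MTD decisions do not use it. The other is that the protocol must add a culture at the Acute Illness Visit. That would be a new procedure, and it would not replace the Day 7 or Day 28 change. The lack of one explains why a rise before treatment may go unseen, but the analysis can be made readable without it.

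**What to change.** In the SAP:

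1. Use the medication changes already recorded at each visit to flag every Day 7 or Day 28 culture taken after a new antibiotic started since Day 1.
2. Show CFU change for all cultures as the main display, and again for unflagged cultures. Do not drop flagged cultures from the main display, because that would remove the subjects who had infections.
3. List antibiotic courses beside each subject's cultures.
4. State that the display is descriptive, and that a fall after a new antibiotic is not read as absence of infectious harm or as an antimicrobial effect.

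The cost is SAP wording and one listing, with no new procedures or data. The downside is sparse cells: under the assumed rates, a flagged cell holds 0 or 1 subject with probability 0.945 to 0.996 in a cohort of 3, and 0.627 to 0.957 among 9. The listing will therefore do most of the work. The unflagged subset is selected on an event after infusion, so it should not be treated as an unbiased estimate of the cells' effect.

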15.4 Analysis of Secondary/Exploratory Endpoints

Although efficacy is not the primary aim of this dose escalation study, changes and patterns of change between MTD and lower doses on inflammatory biomarkers in blood and sputum measured at Baseline, day 7 and day 28 will be explored using a mixed effects model, mean and standard deviation at each time point as well as each patient's case profile will be graphically presented.

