STUDY DESIGN	This will be a prospective, single-center, dose-escalation, open-label interventional study to evaluate the safety and tolerability of allogeneic hMSCs in 15 clinically stable subjects with CF age \geq 18 years. After a two to six week screening period, subjects will have a Baseline visit (Days 1-2) where they will undergo a single intravenous infusion of up to 5×10^6 allogeneic hMSCs/kg of body weight. Infusions will be performed in the Dahms Clinical Research Unit (DCRU) of University Hospitals Cleveland Medical Center. Subjects will be monitored for any infusion related toxicities for 24 hours after the infusion. Subsequent study visits will occur on Days 7, 14, 28, Months 3 and 6 and telephone calls will occur on Days 4 (or 5), 21, 56 and Month 12. Subject safety and tolerability of a single dose of hMSCs will be evaluated at study visits by review of subject diaries, interval history, pulmonary exacerbations (standardized definition in Appendix I), physical examination, spirometry, and analysis of safety laboratories. Special attention will be placed upon detecting pulmonary exacerbations because anti-inflammatory therapies theoretically could suppress the immune system to the point where it leads to increased infectious complications, although MSC therapeutics are proposed to be antimicrobial. In addition to evaluating safety, this study will also explore efficacy end-points for future clinical trials of MSCs in CF including inflammatory biomarkers from blood and sputum. Serum markers (calprotectin, MPO, GM-CSF, IL-1 β , IL-6, IL8, IL-17, and TNF- α) and sputum markers (white cell counts and differentials, IL-1 β ,

	IL-6, IL-8, IL-10, IL-17, GM-CSF, MIP-3 α , TNF- α , and active proteases including neutrophil elastase, α_1 -anti-trypsin, and MMP-9) will be determined at Baseline and on Days 7 and 28 for with-in subject comparison. All subject samples will be archived for future projects. Finally, a diagnostic bone marrow exam will be performed on subjects with CF who consent to undergo the procedure. Bone marrow samples will be banked and used for future translational studies. Study-related procedures are outlined in Appendix II.
PRIMARY OBJECTIVE	To evaluate the infusion-related safety and tolerability of a single allogeneic hMSC infusion in adults with CF.

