1.2 Specific Aim

To determine the safety and tolerability of a single infusion of human MSCs (hMSCs) and to explore secondary efficacy endpoints to determine if hMSCs reduce inflammation in subjects with CF. Markers of inflammation will be measured in blood and sputum before and 7 and 28 days after a single infusion of hMSCs in clinically stable adults with CF.

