
The following treatment regimens will be used:

- Experimental treatment hMSCs at the following doses: 1×10^6 , 3×10^6 or 5×10^6 hMSCs/kg body weight

All subjects who begin an infusion of the investigational product will be considered evaluable for safety and efficacy analyses. Incidence of AEs will be monitored during the trial.

Safety assessments will be based on the incidence of AEs including protocol defined pulmonary exacerbations and changes in lung function, sputum microbiology, safety labs, subject questionnaire, and physical examination. An Acute Illness Visit will be arranged for any subject who experiences any abrupt change in baseline clinical status, between Visit 2 and Visit 5 (the 28 days following infusion) that in the estimation of an investigator, research coordinator, other health care provider or the subject necessitates an in-person office visit.

Total duration of subject participation in the study will be approximately 13 months. Long-term post-treatment follow-up will continue for 12 months after the infusion of the investigational product for each subject. Data on subject survival and on the occurrence of new health problems will be collected from all subjects who receive the investigational product infusion. The information will be gathered during a study visit, a routine clinic visit or via telephone. These data will be collected in the source documents (e.g., subject medical record) and transcribed into an electronic CRF. Any unsuccessful efforts to contact the subject (e.g., dates of unanswered phone calls, failure to show for a clinic visit, etc.) will be documented in the subject's source documents.

Total duration of conducting the study is expected to be approximately 24 months.

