15 STATISTICAL METHODS AND CONSIDERATIONS (BASED UPON PRIMARY AND SECONDARY ENDPOINTS)

Prior to the analysis of the final study data, a detailed Statistical Analysis Plan (SAP) will be written describing all analyses that will be performed. The SAP will contain any modifications to the analysis plan described below.

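### Section 15.4 names only MTD versus lower doses for the biomarkers, a contrast that cannot show a fall common to all doses and fails if the MTD is below the top dose; Section 15.3 leaves the AE groups open to a by-cohort reading (minor)

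*Combined protocol and SAP*

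**What the plan says.** **Aim and endpoint.** Section 1.2 sets out "to explore secondary efficacy endpoints to determine if hMSCs reduce inflammation in subjects with CF". The synopsis says the serum and sputum markers "will be determined at Baseline and on Days 7 and 28 for with-in subject comparison", and Sections 2 and 4.1 also plan a comparison of each subject with their own Baseline. The synopsis and Section 5.2 define the secondary endpoints as changes from Baseline to Day 7 and Day 28. Section 4.1 adds: "All subjects who begin an infusion of the investigational product will be considered evaluable for safety and efficacy analyses".

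**Biomarker analysis.** Section 15.4 takes "changes and patterns of change between MTD and lower doses on inflammatory biomarkers in blood and sputum measured at Baseline, day 7 and day 28" and says these "will be explored using a mixed effects model, mean and standard deviation at each time point", with individual profiles plotted. It gives no model terms and no time contrast. For safety measurements, Section 15.3 says outright that "changes from Baseline and from the previous time point will be summarized at each time point". Section 15.4 has no such sentence for biomarkers.

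**AE analysis.** Section 15.3 says "AEs among dose cohorts will be compared using" Fisher's exact test. Table 1 in Section 8.3.3, whose title uses the term dose cohorts, lists four: three subjects each at 1, 3 and 5x10^6/kg, then six at the MTD.

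**Later SAP.** Section 15 states: "Prior to the analysis of the final study data, a detailed Statistical Analysis Plan (SAP) will be written describing all analyses". It is not among the documents.

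**The concern.** The aim asks whether the cells reduce inflammation. If every dose lowered a marker by the same amount, a contrast between doses would be zero. The one comparison Section 15.4 names therefore does not answer the question in Section 1.2.

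The contrast also depends on where the MTD lands. Section 8.3.3 allows an MTD of 1 or 3x10^6/kg. At the first there is no lower dose. At the second, subjects already given 5x10^6/kg belong to neither side, which sits badly with Section 4.1.

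For AEs, Cohort 4 repeats a dose used earlier. If the Fisher groups are the cohorts of Table 1, two groups share a dose, and a chance difference between them can be read as a difference among doses. At stake is an analyst having to choose the contrast or the grouping after open-label results are known.

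**Working it through.** **Sample size.** Table 1 gives 3 + 3 + 3 + 6 = 15, the stated total. The plan gives no alpha, SD, effect size or AE rate, so those below are assumptions.

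**Who enters the named contrast** (fixed sizes from Table 1; the last row uses the move-down rule of Section 8.1):

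| MTD (x10^6/kg) | At MTD | At lower doses | In neither group |
|---|---|---|---|
| 5 | 9 | 6 | 0 |
| 3 | 9 | 3 | 3 |
| 1 | 9 | none | all treated above 1x10^6/kg |
| 3, after the last three move down from 5 | 6 | 3 | 6 |

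The omissions at 3x10^6/kg assume that subjects had been treated at 5x10^6/kg.

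**Precision.** 95% half-widths for change at one visit, in units of the SD of within-subject change, two-sided 5%:

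- Pooled change, t(n-1)/sqrt(n): n=15, 0.55. If sputum is missing, n=12 gives 0.64 and n=10 gives 0.72.
- 9 v 6: t(13) x sqrt(1/9+1/6) = 1.14.
- 9 v 3: t(10) x sqrt(1/9+1/3) = 1.49.
- 6 v 3: t(7) x sqrt(1/6+1/3) = 2.365 x 0.707 = 1.67.

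**How often the MTD is 1 or 3x10^6/kg.** Assume a traditional 3+3 with the same DLT rate p at each dose. A dose passes with probability s = (1-p)^3 + 3p(1-p)^2 x (1-p)^3. The MTD is 3x10^6 with probability s^2(1-s) and 1x10^6 with probability s(1-s).

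- p=5%: s=0.973; 0.025 + 0.026 = 0.051.
- p=10%: s=0.906; 0.077 + 0.085 = 0.162.
- p=20%: s=0.709; 0.146 + 0.206 = 0.353.

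No dose is tolerated in a further 0.027, 0.094 and 0.291. Section 1.3.4.3.2 reports no infusion toxicity in 43 recipients of 1 to 5x10^6/kg in another disease. The exact 95% upper limit is 1 - 0.025^(1/43) = 8.2%, so the lower rates are the likelier.

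These frequencies should not be paired with the half-widths. A traditional 3+3 expands a dose to six after one DLT. When it ends at 3x10^6/kg, the sizes before Cohort 4 are 3/3/3 only if both lower doses pass at 0/3 and the top dose fails within its first three. At p=5% that is (0.857/0.973)^2 x (0.00725/0.0266) = 0.21, and at p=10% (0.729/0.906)^2 x (0.028/0.0939) = 0.19.

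**AE grouping.** Take the MTD as 5x10^6/kg, and compare cohorts (3,3,3,6) with doses (3,3,9) by full enumeration of the exact Fisher-Freeman-Halton test. There are 4 x 4 x 4 x 7 = 448 outcomes. The two groupings fall on opposite sides of 0.05 in 92 of them: 72 significant only by cohort, 20 only by dose.

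- Probability of disagreement at equal AE rates of 10, 20, 30, 40 and 50%: 0.7, 2.0, 3.0, 3.6 and 3.8%.
- At assumed gradients across the three doses of 5/30/60, 20/50/80, 30/50/70 and 10/10/60%: 12, 16, 10 and 12%.
- Extreme case, 0/3, 0/3, 3/3, 0/6: p=0.0066 by cohort (3 of the 455 equally likely placements) and 0.525 by dose (239 of 455). The whole signal lies within one dose.
- Likeliest disagreement at 5/30/60%, 0/3, 1/3, 2/3, 5/6: p=0.143 by cohort and 0.041 by dose.
- Power by cohort v by dose at those four gradients: 16 v 19, 28 v 40, 12 v 17 and 22 v 21%. Neither grouping always wins.

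**Sections 8.1 and 8.3.3.** Section 8.1 treats three subjects at the MTD and then a final three, which makes the six of Section 8.3.3. The counts agree. The conflict is that Section 8.1 lets the final three move to the next lower dose after two or more DLTs, while Section 8.3.3 gives all six one dose.

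**The case against.** The strongest reply is that Section 15.4 can be read generously. The word changes may stand on its own, with the dose comparison attached only to the patterns of change. Section 15.2 defines Baseline for all analyses, the design sections state the within-subject comparison, and a mixed model with Baseline, Day 7 and Day 28 data can estimate it. This stands in part. A reader might infer that the protocol plans no within-subject analysis at all, and the documents do not support that. What is missing is the contrast, spelled out in the section that governs the analysis.

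A dose comparison is also a defensible aim in an escalation study, and without a control arm change from Baseline is open to regression to the mean. Both points are fair. They argue for keeping a dose comparison and for stating the limit, not for a contrast that can vanish or drop treated subjects.

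On AEs, Section 15.3 opens with three doses, so dose cohort may simply mean dose level. A reader might infer from Table 1 that the test certainly splits a dose. The text allows that reading but does not settle it. No alpha is stated and no decision hangs on this p-value.

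Finally, the promised SAP may modify the plan and could resolve all of this. It will, however, start from Section 15 as written.

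**Conclusion.** The point holds as a minor one. Section 15.4 names a single comparison that is not the endpoint, cannot reveal a common fall, and breaks down when the MTD is below the top dose. It would be wrong to read failure at two of the three possible MTDs as failure in two-thirds of trials. Under a traditional 3+3 with an equal assumed DLT rate, it is about 5% at a 5% rate and 16% at 10%; at 5x10^6/kg the contrast is defined and can include all 15 subjects. The loss of precision is illustrative, for fixed group sizes: half-widths of 1.14 to 1.67 SD against 0.55 SD pooled.

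The AE grouping is ambiguous rather than wrong. It would move the result across 0.05 in 0.7 to 3.8% of trials at equal rates, and in about 10 to 16% under steep assumed gradients.

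A reader might also see Sections 8.1 and 8.3.3 as disagreeing on how many subjects remain. They do not; they disagree on whether the last three may receive a different dose. The analyses concerned are exploratory or descriptive, and the primary safety conclusion is not affected.

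**What to change.** In Section 15 or the promised SAP:

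1. Report mean change from Baseline at Day 7 and at Day 28, with 95% CI, from the planned mixed model, over all infused subjects with samples and per dose. Give the number of sputum samples at each visit, and note that without a control the change cannot be separated from regression to the mean.
2. Replace the MTD versus lower doses contrast with dose by visit, using nominal dose received, so that every treated subject is included whatever the MTD.
3. Define AE groups by each subject's nominal dose received, not by cohort number, with exact 95% CIs (for example 0/3: 0 to 0.708; 3/9: 0.075 to 0.701). This also handles a Cohort 4 that holds two doses. List infusions stopped early, for which Section 8.5 already records the amount given.

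Sections 8.1 and 8.3.3 must be reconciled on the dosing of the final subjects, because this sets the group sizes.

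The cost of items 1 to 3 is three or four sentences. They use data already collected, and nothing in them changes treatment or visits.
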